### 6.5 Interim Analysis

The study will continue during the planned interim analyses.

#### 6.5.1 Planned Interim Analysis

##### 6.5.1.1 *Planned Interim Safety Analysis*

After the first 30 patients complete protocol-specified atezolizumab treatment and undergo the planned surgical resection of their tumor, all safety population subjects at that time will be evaluated for tolerability and safety of the neoadjuvant regimen. If, at the time of the safety interim analysis, three or more patients have experienced Grade 5 adverse events related to protocol treatment, then the study may be discontinued.

Outputs from this SAP which will facilitate the planned interim safety analysis are flagged in Section 9 of this SAP.

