There is not yet extensive data on the safety of thoracic surgical resections after treatment with checkpoint inhibitors. Therefore, after the first 30 patients who complete protocol-specified atezolizumab treatment and have undergone the planned surgical resection of their tumor, the patient cohort will be evaluated for tolerability and safety of the neoadjuvant regimen. If, at the time of the safety interim analysis, three or more patients have experienced Grade 5 adverse events related to protocol treatment, then the study will be discontinued.

Planned Interim Efficacy Analysis

The study includes one interim analysis to assess futility after 90 patients are assessed. The non-binding futility interim boundary satisfies conditional power at a cut-off of 0.30.

LIST OF ABBREVIATIONS AND DEFINITIONS OF TERMS

Abbreviation	Definition
BSA	body surface area
CNB	core needle biopsy
COPD	chronic obstructive pulmonary disease
COVID-19	coronavirus disease 2019
CR	complete response
CRO	contract research organization
CRS	cytokine release syndrome
CT	computed tomography
CTCAE	Common Terminology Criteria for Adverse Events
C _{trough}	trough concentration
DFS	disease-free survival
DLT	dose-limiting toxicity
EBUS	endobronchial ultrasound
EC	Ethics Committee
ECOG	Eastern Cooperative Oncology Group
eCRF	electronic Case Report Form
EDC	electronic data capture
FDA	U.S. Food and Drug Administration
FEV ₁	forced expiratory volume in 1 second
FFPE	formalin-fixed, paraffin-embedded
GGO	ground glass opacity
HLH	hemophagocytic lymphohistiocytosis
HBcAb	hepatitis B core antibody
HBsAg	hepatitis B surface antigen
HBV	hepatitis B virus
HCV	hepatitis C virus
HIPAA	Health Insurance Portability and Accountability Act
HR	hazard ratio
ICH	International Conference on Harmonisation
IF	immunofluorescence
IFN	interferon
IHC	immunohistochemistry
IL	interleukin
IMP	investigational medicinal product
IND	Investigational New Drug (application)
INR	International normalized ratio
ITT	intent-to-treat
IRB	Institutional Review Board

Abbreviation	Definition
IV	Intravenous
IxRS	interactive voice/web response system
K-M	Kaplan-Meier
MAS	macrophage activation syndrome
MRI	magnetic resonance imaging
MTD	maximum tolerated dose
NCCN	National Comprehensive Cancer Network
NCI	National Cancer Institute
NGS	next-generation sequencing
NSCLC	non-small cell lung cancer
ORR	objective response rate
OS	overall survival
PBMC	peripheral blood mononuclear cell

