6. STATISTICAL CONSIDERATIONS AND ANALYSIS PLAN

The objective of this study is to determine if atezolizumab 1200 mg q21d demonstrates efficacy in the neoadjuvant setting by producing a major pathologic response rate of at least 15%; major pathologic response is defined as $\leq 10\%$ of viable tumor cells (Hellmann et al. 2014). Tumors without radiographic response, but which demonstrate a major pathologic response (Hellmann et al. 2014) will be counted as a response.

Safety of atezolizumab in this treatment setting will also be assessed.

Details of the analyses are provided in the Statistical Analysis Plan (SAP).

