6.1 DETERMINATION OF SAMPLE SIZE

The primary objective of this study is to determine the major pathologic response rate. If there is evidence that the major pathologic response rate is at least 15% then there will be further consideration for the testing of atezolizumab in neoadjuvant lung cancer. This is a single-arm study, and all patients will be treated with atezolizumab. The primary endpoint is assessed by a statistical test of a single proportion of responders against the

simple alternative of 5% response. This design provides 95% statistical power to detect a difference of 10% (15% vs. 5%) at a significance level of 0.05 (1-sided test, variance of the test statistic calculated under the alternative hypothesis). To achieve this, approximately 180 patients will be enrolled in this study. At the final analysis (after 180 patients are enrolled), if there are at least 17 patients who respond then the statistical test rejects the null hypothesis of a 5% response rate in favor of a higher response rate.

This study includes one interim analysis to assess futility after 90 patients are assessed. The non-binding futility interim boundary satisfies conditional power of 0.30. Thus, the probability that the statistical test at the final analysis will be significant at the specified power and test level is at least 0.30, conditional on the data available at the time of the interim analysis. At the interim analysis, if there are seven or fewer responders out of 90 patients then the conditional power of the study drops below 0.30, and enrollment into the study may be terminated. [Table 8](#) summarizes the simulated probabilities of stopping at the interim and the final analysis for different values of major pathologic response. Note that simulated probabilities not identical to calculated probabilities due to the discrete nature of response.

Table 8 Simulated Probabilities of Stopping at the Interim and Final analysis for Different Values of Major Pathologic Response

True Major Pathologic Response Rate	Probability of Stopping at Interim	Probability of Continuing to Final	Simulated Power
0.05	0.84	0.16	3%
0.10	0.19	0.81	72%
0.15	0.01	0.99	99%

Note: Simulated probabilities are not identical to calculated probabilities due to the discrete nature of response.

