6.7.1.1 Planned Interim Safety Analysis

There is not yet extensive data on the safety of thoracic surgical resections after treatment with checkpoint inhibitors. Therefore, after the first 30 patients who complete protocol-specified atezolizumab treatment and have undergone the planned surgical resection of their tumor, the patient cohort will be evaluated for tolerability and safety of the neoadjuvant regimen. If, at the time of the safety interim analysis, three or more patients have experienced Grade 5 adverse events related to protocol treatment, then the study will be discontinued.

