6.7.1.2 Planned Interim Efficacy Analysis

The study includes one interim analysis to assess futility after 90 patients are assessed. The non-binding futility interim boundary satisfies conditional power at a cut-off of 0.30.

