### 6.6 Changes to Methods Planned in the Protocol

There is no change in the SAP which is deviate from protocol.

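### SAP 6.5.1.1 says the study *may* stop at three related Grade 5 events where the protocol says it *will*, and SAP 6.6 declares no deviation

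*SAP*

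**What the plan says.** Protocol Section 6.7.1.1 schedules a safety look "after the first 30 patients who complete protocol-specified atezolizumab treatment and have undergone the planned surgical resection of their tumor". It justifies the look by the shortage of data on chest surgery following checkpoint inhibitors. The consequence is unqualified: if "three or more patients have experienced Grade 5 adverse events related to protocol treatment, then the study will be discontinued". The synopsis repeats it: "Grade 5 adverse events related to protocol treatment, then the study will be discontinued".

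SAP 6.5.1.1 describes the same look with the same trigger, but ends differently: if "three or more patients have experienced Grade 5 adverse events related to protocol treatment, then the study may be discontinued". SAP 6.6, the section reserved for departures from the protocol, reads in full: "There is no change in the SAP which is deviate from protocol".

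The protocol words its other planned interim rule, for futility, in another way. Section 6.7.1.2 states: "The non-binding futility interim boundary satisfies conditional power at a cut-off of 0.30". Section 6.1 adds that with seven or fewer responders among 90 the "conditional power of the study drops below 0.30, and enrollment into the study may be terminated". SAP 6.1.4 and 6.5.1.2 carry that rule over with the same non-binding label and the same *may*.

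**The concern.** The protocol gives its two interim rules different force. Futility is expressly non-binding and ends in *may*; safety carries no qualifier and ends in *will*. The SAP gives both rules *may*, so the distinction disappears.

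The word also gives the sponsor nothing useful. Protocol 4.6.3 already lets it terminate the study at any time, including for adverse events. All that *may* adds is the option not to stop once three patients qualify, which is the option the protocol removes.

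At stake is the only study-level safety rule in the plan with a number attached. Protocol 5.1 lists the pre-specified interim safety analysis among the measures that protect patients. Someone preparing or reading the look from the SAP alone would take the stop to be optional and would find in SAP 6.6 an assurance that nothing had changed.

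**Working it through.** There is no figure to reproduce: neither document gives operating characteristics for this rule. The check is a comparison of the texts.

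| Element | Protocol (synopsis; 6.7.1.1) | SAP 6.5.1.1 |
|---|---|---|
| Timing | first 30 patients treated and resected | same |
| Event | Grade 5, related to protocol treatment | same |
| Threshold | three or more patients | same |
| Consequence | *will* be discontinued (2 of 2 statements) | *may* be discontinued (1 of 1 statement) |
| Departures declared | not applicable | none (SAP 6.6) |

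Outcome by number of qualifying patients at the look:

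| Count | Protocol | SAP | Same? |
|---|---|---|---|
| 0, 1 or 2 | rule not triggered | rule not triggered | yes |
| 3 or more | must stop | may stop or continue | no |

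1. Timing, event and threshold match, so both texts lead to the same count. They part only on what must follow a count of three or more.
2. The protocol's *will* does not look accidental. It appears both times the rule is stated, and the same document uses a non-binding label and *may* for futility.
3. The SAP is the text to correct. Protocol Section 6 leaves the detail of the analyses to the SAP, and what follows from a safety trigger is not analysis detail. Under protocol 9.6, changes to the protocol need ethics approval before they take effect, apart from immediate-hazard and purely administrative changes. Protocol 9.2 disallows prospective requests to deviate. An undeclared change of wording in the SAP therefore cannot relax the rule.
4. The patients covered are not in dispute. The SAP refers to everyone in the safety population at that time, and protocol 6.5 already bases the safety analyses on all dosed patients.

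**The case against.** The strongest reply is that nothing would change in practice. The protocol governs conduct, the SAP yields the same count, and the protocol's *will* applies to that count whatever the SAP says. Results also go to a review committee that includes sponsor staff and investigators (protocol 3.1.5 and 9.4), so the decision need not rest on the SAP text alone. On this view it is a one-word drafting slip. That stands as a limit on the impact. A reader might infer that patients would in fact be less well protected; the documents do not show that, since a team following the protocol would stop. The reply does not make the SAP sentence correct.

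A second reply concerns SAP 6.6. The SAP appears to have been drafted on a protocol before Version 7. Footnote l of its schedule of assessments still requires Medical Monitor approval for exceptions, whereas footnote l of protocol Appendix 1 now says only that investigators may discuss them, and the Version 7 list of changes includes removal of such approvals. A reader might infer that SAP 6.6 was untrue when written. That is not shown, because the text examined here does not give the wording of 6.7.1.1 in the version the SAP was written against. The Version 7 changes that are visible do not mention Section 6.7, but that does not settle the matter. What stands is an inconsistency with the protocol as supplied.

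**Conclusion.** The point holds as an inconsistency between the two documents in the plan's only numeric safety stopping rule. It bites only at a count of three or more, where the protocol mandates a stop and the SAP does not. No probability is attached, because the documents give no fatality rate. The conclusion rests on reading an unqualified *will* as mandatory and on the protocol taking precedence over the SAP. The documents do not say whether the 30-patient look has already taken place; if it has, the correction still matters for an accurate record.

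Two stronger readings are tempting but not supported.

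- **That the event means related to atezolizumab only, so that deaths due to the resection do not count.** Some text points that way: protocol 4.3 names atezolizumab as the investigational product, protocol 4.4.1 places resection under concomitant therapy, and SAP 6.4.1 ties *treatment related* to atezolizumab. But the rule uses a different term, *protocol treatment*, and its stated reason is the safety of resection after checkpoint inhibitors. Protocol 5.2.1 includes events related to protocol-mandated interventions among adverse events, and protocol 5.3.4, on combination therapy, speaks of causality for each protocol-mandated therapy. The documents do not support narrowing the trigger.
- **That related deaths after adjuvant treatment starts would be missed, because Table 14.3.1.9.2 is not flagged for the safety look.** Both documents say the look evaluates the neoadjuvant regimen. Table 14.3.1.2a, which covers both study phases, and Listing 16.2.7.1 are flagged for it, so later Grade 5 events would be visible.

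**What to change.** In the last clause of the stopping rule in SAP 6.5.1.1, replace *may* with *will*. That removes the conflict and makes SAP 6.6 consistent with the protocol on this rule. It needs no new data, table, flag or threshold. The only cost is that the sponsor gives up the discretion that the SAP wording implies.

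If the sponsor does want discretion, the route is to amend the synopsis and Section 6.7.1.1 of the protocol, with the approvals that protocol 9.6 requires, and to declare the change in SAP 6.6.

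Leave the definition of the qualifying event as it is: this correction should neither restrict it to atezolizumab nor exclude resection-related deaths.

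A separate clerical slip can be corrected in the same edit. SAP 6.5.1.1 points to a Section 9 for the flagged outputs, but the SAP ends at Section 8 and the flags are in Table 3 of Section 7.

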##### 6.5.1.2 *Planned Interim Efficacy Analysis*

The study includes one interim analysis to assess futility after 90 patients are assessed for MPR. The non-binding futility interim boundary satisfies conditional power at a cut-off of 0.30.

The analysis for the primary endpoint will be conducted and assessed against the futility boundary. If there are 7 or fewer responders out of 90 patients, then the conditional power of the study drops below 0.30, and enrollment may be terminated.

Outputs from this SAP which will facilitate the planned interim efficacy analysis are flagged in Section 9 of this SAP.

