## 5. ANALYSIS POPULATIONS

Data will be summarized using the following analysis populations.

- All Enrolled Subjects: This analysis population will include all enrolled subjects, regardless of whether they received any amount of study drug. The all enrolled subjects population will be used for the summarization of subject disposition.
- Safety Population: This analysis population will include all enrolled subjects who have received any dose of study drug. The safety population will be used for the analysis of safety measures.
- Efficacy Population: This analysis population will include all enrolled patients who have received at least one dose of the study drug and who do not have EGFR or ALK mutant tumors.
- Primary Efficacy Population: This analysis population will include all efficacy population subjects, excluding patients who have not received surgery after neoadjuvant treatment with Atezolizumab, and excluding subjects who have not had a complete resection. This population will be used for primary efficacy analysis. For the primary efficacy population, if major pathological response is unable to be assessed, then it will remain undetermined and the subject will be removed from this population.

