#### **6.1.4 Determination of Sample Size**

The primary objective of this study is to determine the major pathological response rate. If there is evidence that the major pathologic response rate is at least 15% then there will be further consideration for the testing of atezolizumab in neoadjuvant lung cancer. This is a single-arm study, and all patients will be treated with atezolizumab. The primary endpoint is assessed by a statistical test of a single proportion of responders against the simple alternative of 5% response.

This design provides 95% statistical power to detect a difference of 10% (15% vs. 5%) at a significance level of 0.05 (1-sided test, variance of the test statistic calculated under the alternative hypothesis). To achieve this, approximately 180 patients will be enrolled in this study. At the final analysis (after 180 patients are enrolled), if there are at least 17 patients who respond then the statistical test rejects the null hypothesis of a 5% response rate in favor of a higher response rate.

This study includes one interim analysis to assess futility after 90 patients are assessed. The non-binding futility interim boundary satisfies conditional power of 0.30. Thus, the probability that the statistical test at the final analysis will be significant at the specified power and test level is at least 0.30, conditional on the data available at the time of the interim analysis. At the interim analysis, if there are seven or fewer responders out of 90 patients then the conditional power of the study drops below 0.30, and enrollment into the study may be terminated.

Differential response by PD-L1 status (positive versus negative) will be assessed. While the composition of PD-L1 status in this patient population is not known, the study will aim to include at least 60 PD-L1 positive patients. With 60 PD-L1 positive patients, the one-sided 95% CI excludes 20% if the major pathologic response rate is 30% (18 responders out of 60 patients). Final enrollment numbers may be expanded accordingly.

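### The printed decision counts (reject at 17 or more, futility at 7 or fewer of 90) are not indexed to the primary efficacy population and do not agree with the SAP's exact test

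*SAP*

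**What the plan says.** **Final count.** Protocol 6.1 states: "At the final analysis (after 180 patients are enrolled), if there are at least 17 patients who respond then the statistical test rejects" the 5% null. SAP 6.1.4 repeats the rule. Both sections claim 95% power for 15% against 5% at one-sided 0.05, using the variance under the alternative. Neither gives an allowance for patients who leave the analysis set.

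**Interim count.** SAP 6.5.1.2 states: "The study includes one interim analysis to assess futility after 90 patients are assessed for MPR". It then states: "If there are 7 or fewer responders out of 90 patients, then the conditional power of the study drops below 0.30". The boundary is non-binding, and the section compares the primary endpoint analysis with it.

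**Population.** SAP 5 defines the primary efficacy population: "This analysis population will include all efficacy population subjects, excluding patients who have not received surgery after neoadjuvant treatment with Atezolizumab". It also leaves out incompletely resected patients and those whose response cannot be scored. The efficacy population from which it is drawn has already dropped EGFR- and ALK-mutant tumors.

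**Test.** SAP 6.3.1 specifies a one-sample exact binomial test of 5% in the primary efficacy population. It names no fixed count.

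**The concern.** The two counts are the trial's only numerical efficacy decision rules. One is attached to patients enrolled and the other to patients scored for response; the primary test uses neither group.

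EGFR and ALK mutations are not exclusion criteria (Protocol 4.1.2). A mutant patient can therefore be enrolled, resected and scored, yet lie outside the primary analysis. The same holds at the interim for an incompletely resected patient. The primary efficacy population can thus be below 90 at the interim and below 180 at the end, while 7 and 17 stay as printed.

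A fixed count on a smaller denominator is a stricter rule. It makes rejection harder and futility stopping more likely at the response rate the trial is meant to detect. It also leaves room to choose the denominator after responses are known, in an open-label study.

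**Working it through.** **Inputs.** Null rate 5%, target 15%, one-sided alpha 0.05, counts 17/180 and 7/90 (Protocol 6.1, SAP 6.1.4, SAP 6.5.1.2). The documents give no attrition rate. I assume 10%, 15% and 20% lost from 180, so N = 162, 153 and 144. At the interim I assume 10% of the 90 scored patients lie outside the primary population, leaving 81.

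**1. Reproducing the plan's figures.**
- Count 17: 180 × (0.05 + 1.645 × √(0.15 × 0.85 / 180)) = 16.9, so 17 comes from a normal approximation with alternative variance.
- Sample size from the same formula: 0.1275 × ((1.645 + 1.645) / 0.10)² = 138. Enrolling 180 leaves room for 23% loss (1 − 138/180).
- Power of the printed rule with the stop followed: sum over x > 7 of P(X₁ = x | 90, 0.15) × P(X₂ ≥ 17 − x | 90, 0.15) = 96.4%. This is consistent with 95%. Without the stop it is 98.9%.
- Futility count: conditional power under the current trend is P(Bin(90, x/90) ≥ 17 − x), which is 0.16 at x = 7 and 0.41 at x = 8. So 7 reproduces when 17 are needed and the observed rate is assumed to continue. At the 15% design rate it would be P(Bin(90, 0.15) ≥ 10) = 0.89. The assumed rate therefore matters, and the plan does not state it.

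**2. Exact test at full N.** The critical count is the smallest r with P(X ≥ r | N, 0.05) ≤ 0.05. At N = 180, r = 15 (alpha 0.037); a count of 17 has alpha 0.009. The SAP test and the printed rule therefore disagree at 15 or 16 responders even with no attrition. With 15 needed, conditional power at 7/90 is P(Bin(90, 7/90) ≥ 8) = 0.40, and at 6/90 it is 0.15. The statement that it is below 0.30 at 7 then fails.

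Protocol Table 8 points the same way. It prints stopping probabilities of 0.84, 0.19 and 0.01, and power of 3%, 72% and 99%, at true rates of 5%, 10% and 15%. The rule 6/90 with 15/180 gives 0.836, 0.193, 0.013 and 2.9%, 72.2%, 98.6%. The printed 7/90 with 17/180 gives 0.92, 0.31, 0.03 and 0.7%, 54%, 96%.

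**3. Final analysis on a smaller N, true rate 15%, no futility stop.**

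| N | Exact critical count | Exact-test power | Power if 17 is kept |
|---|---|---|---|
| 180 | 15 | 99.7% | 98.9% |
| 162 | 14 | 99.4% | 96.2% |
| 153 | 13 | 99.4% | 93.3% |
| 144 | 13 | 98.8% | 88.6% |

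Holding 17 gives less than 95% at N ≤ 157. The exact test gives at least 95% at every N from 102 to 180.

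**4. Interim on fewer than 90 primary-population patients.** P(X ≤ 7 | n, 0.15) is 3.1% at n = 90 and 6.7% at n = 81. With 7 applied to 81, the stop followed and the exact test at the end, power is 93.0% (N = 144, count 13) or 93.2% (N = 162, count 14). Current-trend conditional power at 7/81 is P(Bin(63, 7/81) ≥ 6) = 0.47 for N = 144 and P(Bin(81, 7/81) ≥ 7) = 0.56 for N = 162. On that denominator the count of 7 recommends stopping where the 0.30 criterion says continue.

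**The case against.** A reader might infer that the trial does not deliver its 95% power. The documents do not support that.

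- The SAP's primary test is exact and uses the achieved N, so its critical count falls as N falls. No text says to apply 17 at any N other than 180.
- The plan's own formula needs 138 patients, so 180 already contains a margin, although it is not described as one.
- Futility is non-binding and enrolment only may be stopped. Every power loss through the interim assumes that the stop is followed.
- Incompletely resected patients are to be replaced (Protocol 3.1.2).
- The interim 90 are already scored for response, and SAP Table 3 assigns the primary response table, at the efficacy interim, to the primary efficacy population. Ninety evaluable patients is thus a natural reading. On it, the exact test with the 7/90 stop followed gives 96.7% at N=162 and 96.4% at N=144.
- A milder interim shortfall, 86 patients with final N=162, still gives 95.4% with the exact test and the stop followed.

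All of this stands, and it limits the point to how the counts are printed. It does not remove it. SAP 6.1.4 and 6.3.1 still give different rejection rules. SAP 6.5.1.2 never says that the 90 must belong to the primary efficacy population. Withdrawals and early treatment discontinuations are not replaced (Protocol 4.6.1 and 4.6.2), so some shrinkage is to be expected.

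**Conclusion.** The counts should be corrected; the design's power is not shown to be inadequate. The firm part needs no attrition assumption: at N=180 the printed 17 disagrees with the exact-test count of 15, and 7 of 90 does not meet the 0.30 criterion once 15 is the target (0.40 under the current trend).

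The rest is conditional. If 17 is held on a smaller primary population, power drops to 93.3% at N=153 and 88.6% at N=144, and 13 to 16 responders at N=144 would be significant by SAP 6.3.1 but fall short of the count in SAP 6.1.4. If 7 is applied to 81 primary-population patients and the stop is followed, power is about 93%. The values 162, 153, 144 and 81 are assumptions, because the documents give no expected attrition. Severity: should-fix.

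**What to change.** 1. In SAP 6.1.4 and Protocol 6.1, replace the fixed count of 17 with the exact binomial test at the achieved primary-efficacy-population N. Print its critical counts: 15 at 180, 14 at 162, 13 at 144, 12 at 126–140.
2. In SAP 6.5.1.2, trigger the interim when 90 primary-efficacy-population patients have a pathologic response result. Re-derive the non-binding futility count as conditional power below 0.30 against the exact-test critical count, and state the response rate assumed for the remaining patients.
3. State that the 95% power refers to the primary efficacy population, and give the power at its expected N.

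The cost is wording in the two documents and an interim that may fall slightly later. No extra enrolment is needed.
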